Patients indicated and scheduled for a shoulder arthroscopy will be identified from faculty surgeon case logs at the NYU Langone Health, Langone Orthopedic Hospital Sports Medicine Division. After informed consent is obtained, a chart review of patients' medications and past medical histories will be performed based on their electronic medical records to identify any current pain medications or exclusion criteria. In order to maintain the blind, another surgeon not involved in the procedure will randomize the patient to one of two cohorts using REDCap. Both surgeons are members of the study team. The randomization will be block randomization, via a computer generator on RedCap.

- Cohort 1: CBD ODTs to be administered with routine post-operative pain management regimen
- Cohort 2: Will not receive CBD; but a visually indistinguishable placebo ODT instead.

The resident physician, physician assistant, anesthesiologist, surgeon and study team members will remain blinded. Additionally, all patients will receive a traditional upper extremity interscalene block as per routine.

Immediate post-operative management will not be affected by this study. All patients will receive a standardized regimen of Percocet for pain management, which is standard of care post-operative treatment. Patients will receive a standard dose of 5/325mg and be discharged with 30 tabs and will be instructed to take 1-2 tablets, as needed, every 4-6 hours.

Additionally, patients will be randomized into one of two cohorts. The first cohort will receive a 25mg CBD ODT, every 4-6 hours as needed, with instructions to take two CBD ODTs if they weigh more than 80 kg (total maximum of 50mg per dose every 4-6 hours as needed). Cohort 2 will receive the same instructions, but with the placebo ODT instead. The dose of 25mg for subjects weighing \geq 80kg and 50mg for subjects weighing more than 80kg was selected based on recommendations from the FDA.

The use of cannabidiol (CBD) in pain reduction and opioid use after shoulder arthroscopy. A Double-Blind, Randomized Control Study

Version 06/28/2022

All subjects will be required to refrain from use of THC, or other cannabis-related products for the duration of the study.

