Planned safety monitoring during the duration of the study will include monitoring for liver function, laboratory abnormalities and suicidality assessments throughout the study and for follow-up visits. Liver function tests, including serum transaminase and bilirubin, will be obtained on Day 2, Day 7, and Day 14. Elevated liver transaminase and bilirubin levels will be grounds for immediate removal from the study. C-SSRS will be assessed at baseline, Day 7, and Day 14 by the surgeon. Although CBD does not increase risk of suicidal ideation and behavior, this is being done in accordance with FDA recommendation for clinical trials involving drugs with CNS activity. If subjects are found to pose a risk to themselves, standard institutional procedures will be followed to refer subjects for appropriate care, including emergency care if needed.

The maximum CBD dose given to any subject will be less than 2mg/kg/day, well below levels associated with any hepatic risk (Iffland & Grotenherman, 2017).

The use of cannabidiol (CBD) in pain reduction and opioid use after shoulder arthroscopy. A Double-Blind, Randomized Control Study

Version 06/28/2022

CBD was not deemed to increase the severity of Percocet's opioid toxicities, as they act on different pathways. There is a potential for CBD to work in the same C450 cytochrome pathway as the acetaminophen, and thus no additional acetaminophen is to be prescribed outside of this, which is well below the maximum prescribing threshold of 4g per day.

The patients will stay in the recovery unit until cleared for discharge by an anesthesiologist. They will be prohibited from driving or operating a motor vehicle for 2 hours following their first dose of the study drug.

Patients will be educated on the importance of keeping the study drug in a safe place at all times and ensure it is not accessible to anyone other than themselves.

Additionally, all patients will be de-identified and given a code. Information linking the patient codes to the participants' names and medical record numbers will be stored in a secure location separate from the medical information. Access to the information linking the linkage codes with participant identifiers shall be restricted.

Potential Benefits to the Subjects

Patients may experience less pain post-operatively, and may require less narcotics use, which has a steeper side-effect profile. However, these benefits cannot be guaranteed.

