Additionally, it is the hope of the research team that results of this study will benefit future patients and their physicians by providing more information regarding the use of CBD after surgery. This will allow for a more open and informed dialogue, and possibly a change standard of care treatment.

Drug Shipment, Storage, Dispensing, Accountability, and Destruction: The CBD and matching placebo ODTs will be shipped to the NYU Langone Health Research Pharmacy in bottles labeled CBD or Placebo 25mg ODT with the subject #, date of dispensing and # of ODTs. Subjects will be dispensed enough 25mg ODTs for a maximum dose of every 4-6 hours for 14 days (subjects weighing over 80kg will be dispensed twice the amount of ODTs to account for 2 ODTs per dose (a total of 50mg CBD or placebo per dose). Subjects will be reminded that they should take the CBD or placebo ODT orally, every 4-6 hours, as needed for 14 days. The dates and times the ODT is taken are to be recorded in the subject's diary. Subjects will need to bring the drug with them (including empty and unused bottles) to the site for their Day 7 and Day 14 visits for accountability. Any remaining drug will be collected at Day 14 and destroyed per NYULH Research Pharmacy SOP.

V. INVESTIGATOR'S QUALIFICATIONS AND EXPERIENCE

The CV, medical license, and human subjects' tutorial completion report are attached for all investigators who are participating in this study. All research personnel have medical research experience and are qualified to participate in this quality study. Most importantly, staff have been properly educated and certified with CITI training to conduct research in a matter that will maintain full patient confidentiality. The research coordinator for this study is trained in GCP

principles and practices and will be responsible for compliance with GCP guidelines for all study investigators and research assistants.

VI. SUBJECT IDENTIFICATION, RECRUITMENT AND CONSENT/ASSENT

Method of Subject Identification and Recruitment

Appropriate patients, who meet all of the inclusion criteria and none of the exclusion criteria, who require a shoulder arthroscopy, will be identified from the clinical offices of the investigator surgeons.

Process of Consent

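### The stated CBD ceiling of under 2 mg/kg/day does not follow from the dosing and dispensing rules, which permit 2.5 to 3.75 mg/kg/day just above 80 kg

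*Combined protocol and SAP*

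**What the plan says.** Three places in the combined protocol and SAP bear on the daily dose.

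- **Section IV, Protection against Risks**, gives the safety figure: "The maximum CBD dose given to any subject will be less than 2mg/kg/day, well below levels associated with any hepatic risk".
- **Section III, Methods and Procedures**, gives the dosing rule: "The first cohort will receive a 25mg CBD ODT, every 4-6 hours as needed". Subjects above 80 kg take two tablets each time. The only maximum there is per dose: "total maximum of 50mg per dose every 4-6 hours as needed". The placebo arm has the same instructions.
- **Section IV, Drug Shipment, Storage, Dispensing, Accountability, and Destruction**, sets the supply: "Subjects will be dispensed enough 25mg ODTs for a maximum dose of every 4-6 hours for 14 days", and "subjects weighing over 80kg will be dispensed twice the amount of ODTs to account for 2 ODTs per dose". Subjects are reminded that "they should take the CBD or placebo ODT orally, every 4-6 hours, as needed for 14 days".

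No section states a cap on doses per day, a cap on milligrams per day or a minimum body weight.

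One sentence in section III prints the lower weight band with a greater-or-equal sign at 80 kg. This looks like a slip for less-or-equal. The rule for subjects above 80 kg is clear from the surrounding text, so the sign does not affect the point.

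**The concern.** The safety statement is categorical. It gives a maximum, applies it to any subject, and uses it as the dose-based argument that hepatic risk is not a concern. The dosing rule fixes the amount per dose and a range of spacing, so a daily maximum follows from it, and that maximum is not below 2 mg/kg/day at many ordinary adult weights.

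If the figure was meant as a calculated maximum, it is wrong. If it was meant as a limit, it does not appear in the protocol's dosing instruction or in the quantity dispensed. Either way, a subject who follows the written instruction exactly can pass the ceiling, and no section says at how many doses that happens.

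The protocol itself lists hepatic toxicity as a rare side effect of CBD (section IV, Risk). It also notes a possible shared metabolic pathway with acetaminophen, which every subject is given in Percocet. The dose ceiling is therefore one of the stated hepatic protections.

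**Working it through.** **Inputs.** 25 mg per dose up to 80 kg and 50 mg above 80 kg, spaced 4 to 6 hours (section III); 14 days' supply at that rate, doubled above 80 kg (section IV, dispensing paragraph); ceiling of under 2 mg/kg/day (section IV, Protection against Risks).

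**Formula.** Maximum mg/kg/day = (mg per dose × doses per day) / weight in kg. Doses per day run from 24/6 = 4 to 24/4 = 6. Five doses (24/5 = 4.8 h apart) also fit the range.

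**Can the stated figure be reproduced?** The protocol shows no derivation. Above 80 kg the figure holds for every subject only at three doses a day: 3 × 50 = 150 mg/day, and 150/80 = 1.875 mg/kg/day. At 80 kg with 50 mg doses, the ceiling corresponds to 2 × 80/50 = 3.2 doses a day. Three evenly spaced doses means every 8 hours, which is outside the written range. The longest permitted spacing, every 6 hours, already gives four.

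**Permitted daily totals, and the weights at which they reach or pass 2 mg/kg/day** (weight = daily mg / 2):

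| Doses/day | 25 mg doses: mg/day | Reached at weights | 50 mg doses: mg/day | Reached at weights |
|---|---|---|---|---|
| 4 | 100 | up to 50 kg | 200 | above 80 to 100 kg |
| 5 | 125 | up to 62.5 kg | 250 | above 80 to 125 kg |
| 6 | 150 | up to 75 kg | 300 | above 80 to 150 kg |

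**Examples.**
- Just above 80 kg (limiting values): 200/80 = 2.50 and 300/80 = 3.75.
- 81 kg: 200/81 = 2.47 and 300/81 = 3.70.
- 90 kg, four doses: 200/90 = 2.22.
- 100 kg, six doses: 300/100 = 3.00.
- 60 kg, six doses: 150/60 = 2.50.
- 40 kg, six doses: 150/40 = 3.75. The figure is higher still below 40 kg, since no minimum weight is set.

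**Supply.** The protocol gives no tablet count, so these figures are derived from its rule. Above 80 kg, 14 days needs 2 × 4 × 14 = 112 to 2 × 6 × 14 = 168 tablets. At 81 kg the ceiling over 14 days corresponds to 2 × 81 × 14 = 2,268 mg, and 2,268/25 = 90.7, so at most 90 tablets. The supply is 112/90.7 = 1.23 to 168/90.7 = 1.85 times that allowance.

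**The case against.** The strongest reply is that the drug is taken as needed, so few subjects would dose around the clock, and real intake may well stay under 2 mg/kg/day. That may be so, but the sentence claims a maximum, not an expected intake.

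Nor does sleep settle it. Skipping nights at six-hour spacing could bring a subject to three doses (150/81 = 1.85 mg/kg/day at 81 kg), but nothing limits dosing to waking hours. At the permitted four-hour spacing, four doses fit within 12 hours, and four already give 2.47 mg/kg/day at 81 kg.

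Other objections have some force:

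- **Other safeguards exist.** There are exclusions for abnormal liver tests, cirrhosis and moderate or severe hepatic impairment, baseline liver enzymes and GGT, on-study liver tests, and removal for elevated values. The diary and drug counts would also show high intake. These reduce the consequence but do not make the figure correct. The Day 2 liver test appears in Protection against Risks and is implied by the withdrawal criteria, but not in section III or the time-point table, so it cannot be relied on.
- **Section III says the 25 mg and 50 mg doses follow FDA recommendations.** That supports the amount per dose, not a daily total.
- **The consent form and diary text are not visible,** so a cap could be stated there. What can be said is that no section of the protocol states one. The dispensing rule conflicts with the ceiling whatever those materials say.
- **No harm is shown.** This is right. Whether 2 to 3.75 mg/kg/day carries hepatic risk cannot be judged from the documents.

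**Conclusion.** The point holds, with high confidence. A stated safety maximum is contradicted by the trial's own dosing and dispensing rules. Even on the most lenient reading (six-hourly), subjects above 80 kg and up to 100 kg, and those up to 50 kg, reach or pass 2 mg/kg/day. At four-hourly dosing the ceiling is met only above 75 to 80 kg and above 150 kg.

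This rests on taking the 4-to-6-hour spacing as written, over a 24-hour day, with no cap elsewhere. The documents give no weight distribution, so the share of subjects affected cannot be stated. The primary analysis is not touched. The error must still be corrected, because the figure is the protocol's stated dose-based assurance on hepatic risk.

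**What to change.** Choose one of the following and make the dosing text, the dispensing paragraph and the hepatic-risk sentence agree. The choice belongs to the sponsor's clinicians.

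**A. Keep the ceiling and add a daily cap, identical in both arms to protect the blind.**

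- *Flat cap of three doses a day (simplest).* This gives at most 3 × 25 = 75 mg/day up to 80 kg and 150 mg/day above, and stays under 2 mg/kg/day for everyone above 75/2 = 37.5 kg. Dispense 3 × 14 = 42 tablets, or 84 above 80 kg.
- *Cap by weight band*, which keeps more of the permitted exposure. Both dose levels stay under 2 mg/kg/day at these maxima:

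| Maximum doses/day | 25 mg doses | 50 mg doses |
|---|---|---|
| 3 | above 37.5 to 50 kg | above 80 to 100 kg |
| 4 | above 50 to 62.5 kg | above 100 to 125 kg |
| 5 | above 62.5 to 75 kg | above 125 to 150 kg |
| 6 | above 75 to 80 kg | above 150 kg |

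Either form needs a minimum weight or a lower cap at or below 37.5 kg. The cost is a lower permitted maximum, which may reduce the exposure being tested: above 80 to 100 kg it falls from 200–300 to 150 mg/day. The flat cap cuts more at other weights; the banded cap adds a table to the patient instructions.

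**B. Keep the dosing and correct the statement.** Give the maximum as up to about 3.75 mg/kg/day just above 80 kg (also at 40 kg, and higher below that unless a minimum weight is set), and revise the hepatic-risk wording with support for that level. If subjects have already been dosed, this leaves treatment the same across subjects. The cost is a less favourable figure and the need for fresh support for the hepatic claim.

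Either is a short amendment, and the weight-band sign in section III can be corrected at the same time.

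### The stated CBD maximum of under 2 mg/kg/day is not guaranteed by the regimen, which permits up to about 3.75 mg/kg/day just above 80 kg

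*Combined protocol and SAP*

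**What the plan says.** Section IV, Protection against Risks, gives a daily ceiling for every participant and bases a hepatic-safety statement on it: "The maximum CBD dose given to any subject will be less than 2mg/kg/day, well below levels associated with any hepatic risk".

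The dose itself is set in section III, Methods and Procedures: "The first cohort will receive a 25mg CBD ODT, every 4-6 hours as needed". Heavier patients get a doubled dose, under the rule "with instructions to take two CBD ODTs if they weigh more than 80 kg". The only limit given there applies to a single dose: "total maximum of 50mg per dose every 4-6 hours as needed". The placebo arm follows the same instructions.

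The supply is set in section IV, in the paragraph on drug shipment, storage, dispensing, accountability and destruction: "Subjects will be dispensed enough 25mg ODTs for a maximum dose of every 4-6 hours for 14 days". For the heavier group it adds that "subjects weighing over 80kg will be dispensed twice the amount of ODTs to account for 2 ODTs per dose". That paragraph repeats the as-needed schedule as the reminder to patients and adds no limit on doses or milligrams per day.

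Weight is recorded before surgery, but no eligibility criterion sets a lower or upper weight.

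**The concern.** The ceiling is in mg/kg/day, while the regimen is a fixed dose in two weight groups with a minimum interval. Whether the ceiling holds depends on dose, number of doses per day and body weight. The protocol limits only the first directly. The interval allows four to six doses a day, and nothing in the dosing, dispensing or patient instructions turns the ceiling into a number of tablets.

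The figure carries weight in the risk assessment. Section IV lists hepatic toxicity as a rare effect of CBD. It also notes that CBD may share a metabolic pathway with acetaminophen, which every patient receives in Percocet. Anyone judging risk from this sentence is given a maximum that a patient can exceed while following the dosing instructions exactly. Whether that would count as a protocol deviation is unclear, because one part of the protocol would be met and another contradicted.

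**Working it through.** **Inputs**
- Ceiling: under 2 mg/kg/day (section IV, Protection against Risks).
- Dose: 25 mg up to 80 kg, 50 mg above 80 kg (section III).
- Interval: 4 to 6 hours as needed (section III and the dispensing paragraph).
- Duration of supply: 14 days (dispensing paragraph).
- Body weights: 60 kg and 81 kg are illustrative assumptions.

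The sentence in section III that explains the dose choice prints a sign before 80 kg for the 25 mg group that conflicts with the rest of the same sentence. I read it as 80 kg or less, in line with the dosing instruction and the dispensing paragraph. This may be a text-reading artefact, and the result does not depend on it.

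**Formulas**
- Doses per day = 24 / interval: 24/6 = 4 and 24/4 = 6.
- mg/kg/day = doses per day × mg per dose / weight.
- Weight at which intake equals the ceiling = daily mg / 2. At or below this weight the ceiling is not met.

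**Daily maxima**

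| Group | Interval | mg/day | Under 2 mg/kg/day only above | Example |
|---|---|---|---|---|
| Up to 80 kg (25 mg) | 6 h | 4 × 25 = 100 | 100/2 = 50 kg | 100/60 = 1.67 at 60 kg |
| Up to 80 kg (25 mg) | 4 h | 6 × 25 = 150 | 150/2 = 75 kg | 150/60 = 2.50 at 60 kg |
| Above 80 kg (50 mg) | 6 h | 4 × 50 = 200 | 200/2 = 100 kg | 200/81 = 2.47 at 81 kg |
| Above 80 kg (50 mg) | 4 h | 6 × 50 = 300 | 300/2 = 150 kg | 300/81 = 3.70 at 81 kg |

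The stated figure therefore cannot be reproduced as a maximum for any subject. The permitted peak just above 80 kg approaches 300/80 = 3.75 mg/kg/day. The 25 mg dose reaches the same value at 150/3.75 = 40 kg and would exceed it below that weight.

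**Supply for 14 days**
- Up to 80 kg: 4 × 14 = 56 to 6 × 14 = 84 tablets.
- Above 80 kg: double, 112 to 168 tablets.
- Even the lower count above 80 kg supports 112 × 25 / 14 = 200 mg/day, which is 2 mg/kg/day or more up to 100 kg.

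**What a daily cap would need to be**
- Three doses at 50 mg: 150 mg/day, below 150/80 = 1.875 mg/kg/day for everyone above 80 kg.
- Three doses at 25 mg: 75 mg/day, under 2 mg/kg/day above 75/2 = 37.5 kg.
- Four doses at 50 mg do not meet the ceiling: 200/81 = 2.47.

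**The case against.** The strongest reply is that dosing is as needed, so few patients may come near these totals, and that some groups stay under the ceiling whatever they do. Both points are true. Patients above 75 and up to 80 kg, and those above 150 kg, comply at any permitted interval, and those above 50 and up to 80 kg comply if they dose every 6 hours. But the sentence is about the maximum for any subject, so the permitted maximum is the right test. Reaching it does not require night-time dosing: four doses 4 hours apart, say 07:00, 11:00, 15:00 and 19:00, already give 200 mg above 80 kg.

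A second reply is that the ceiling sentence is itself protocol text and so acts as the cap. It is a cap in words, but no instruction to the patient, prescriber or pharmacy applies it. The diary, and the tablet counts at Days 7 and 14, can show an excess only afterwards.

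A third is that the ceiling is one of several hepatic protections. The protocol excludes patients with abnormal liver tests, cirrhosis or Child-Pugh B or C impairment, takes baseline enzymes, tests liver function during the study, removes patients with elevated values, and limits exposure to 14 days. This bears on how serious the gap is. It does not make the dose statement true. Section IV also lists a Day 2 liver test that the Methods text and the time-point table do not schedule.

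Finally, section III says the two doses follow FDA recommendations. That supports the amounts per dose and suggests that the ceiling sentence, not the regimen, may be the error. It affects which remedy is better, not whether one is needed.

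**Conclusion.** The concern holds as an internal inconsistency in a safety figure. The regimen permits up to about 3.75 mg/kg/day just above 80 kg, nearly twice the stated ceiling. Patients above 80 and up to 100 kg reach or exceed the ceiling even at the longest permitted interval if they dose round the clock.

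This assumes that patients may use every dose the interval allows, and that the weight rule is one tablet up to 80 kg and two above. It makes no claim about actual intake. Nor does it show that 2.5 to 3.75 mg/kg/day is harmful to the liver: the protocol's support for its margin is a cited review that was not available here. The contradiction is certain; its clinical consequence is not established.

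**What to change.** Choose one of two.

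1. **Cap the daily dose.** State a maximum number of doses per 24 hours in section III, in the patient reminder and in the dispensing quantities. The simplest rule is three doses per 24 hours, which meets the ceiling for anyone above 37.5 kg. Supply becomes 3 × 14 = 42 tablets up to 80 kg and 84 above 80 kg, against 56 to 84 and 112 to 168 now. If three is thought too few for some weights, the largest compliant numbers are:
   - 25 mg dose: 3 above 37.5 and up to 50 kg, 4 above 50 and up to 62.5 kg, 5 above 62.5 and up to 75 kg, 6 above 75 and up to 80 kg.
   - 50 mg dose: 3 above 80 and up to 100 kg, 4 above 100 and up to 125 kg, 5 above 125 and up to 150 kg, 6 above 150 kg.

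2. **Keep the regimen and correct the statement.** Give the maximum as up to about 3.75 mg/kg/day for anyone of at least 40 kg, and justify the hepatic-safety claim at that level.

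The second option costs one corrected sentence and its justification. The first needs little text and new dispensing counts, but it reduces the permitted exposure under the IND, so it is a change of treatment and not only of wording. In either case, check the sign before 80 kg in the dose-rationale sentence of section III against the source file.
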